5.1.1. Scoring rules and handling of individual item missing data

Measure	Scoring	Treatment of missing data
PHQ9	Sum of items	Imputation based on mean of remaining items if number of missing items ≤ 2
ALS	sum of three subscales (elation, anxiety, anger); sum of these to give total score	Imputation of subscale score based on mean of remaining items if less than 25% of items are missing
ASRM	Sum of items	Imputation based on mean of remaining items if number of missing items > 2
BRQ	Sum of items (with reversal of selected items)	Imputation based on mean of remaining items if number of missing items < 9 .
QoL.BD	Sum of items	Imputation based on mean of remaining items if number of missing items < 3 .
GAD7	Sum of items	Imputation based on mean of remaining items if number of missing items > 2 .

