3.3. Study populations

Analyses will use observed data only (i.e. without imputation). Data on session attendance rates will separate out any participants who left the study before the pre-treatment point and thus did not reach the point in the study where therapy commenced.

4. Trial population

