5.1. Outcome definitions

Means of assessing primary (feasibility) outcomes

1. Safety will be measured by rates of therapy-related adverse events across the study period, and rates of reliable deterioration from the pre-treatment point on the Patient Health Questionnaire (PHQ), Altman Scale for Rating Mania (ASRM), Affective Lability Scale (ALS), Generalised Anxiety Disorder questionnaire (GAD), Quality of Life in Bipolar Disorder scale (QoL.BD) and Bipolar Recovery Questionnaire (BRQ) at 7 months (30 weeks) follow-up.
2. Acceptability will be measured by therapy uptake and completion rates across the study period, and quantitative and qualitative feedback from participants and therapists at the post-therapy point.
3. Potential of the intervention to deliver benefit will be measured by rates of reliable, and reliable and clinically significant, change in the Patient Health Questionnaire and the bipolar-depression scale of the Affective Lability Scale, from the baseline period (mean score) to the 3 week post-therapy period (mean score).

Secondary outcome measures

1. Rates of reliable, and reliable and clinically significant, change on the following measures: Bipolar Disorder Recovery Questionnaire, Quality of Life in Bipolar Disorder Scale and Generalised Anxiety Disorder assessment scale from pre-therapy to 7-month follow-up.
2. Rates of reliable, and reliable and clinically significant, change on the Altman Scale for Rating Mania from the baseline period (mean score) to the 3 week post-therapy period (mean score).
3. Group-level change in PHQ, ALS, ASRM, BRQ, QoL.BD, GAD from baseline to 6-month follow-up and pre-therapy to 7-month follow-up.
4. Mood instability will be measured (in addition to the ALS) by a visual analogue scale of mood at five timepoints per day for 14 days on two occasions (pre and post therapy) for each participant. This allows for the calculation of mood instability before and after therapy.

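### The missing-item rule for ASRM and GAD-7 is the wrong way round: totals are filled in only when more than two items are blank

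*SAP*

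**What the plan says.** The table in SAP Section 5.1.1 gives one missing-item rule per measure. The ASRM and GAD7 rows carry the same words: "Imputation based on mean of remaining items if number of missing items > 2". The other four rows read:

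- PHQ9: "Imputation based on mean of remaining items if number of missing items ≤ 2"
- ALS: "Imputation of subscale score based on mean of remaining items if less than 25% of items are missing"
- BRQ: "Imputation based on mean of remaining items if number of missing items < 9"
- QoL.BD: "Imputation based on mean of remaining items if number of missing items < 3"

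Section 5.1 puts both affected scales in the primary safety outcome. That outcome includes "rates of reliable deterioration from the pre-treatment point on the Patient Health Questionnaire (PHQ), Altman Scale for Rating Mania (ASRM") and goes on to list the ALS, GAD, QoL.BD and BRQ, all assessed at 7 months. GAD also enters the first secondary outcome and ASRM the second, and both enter the group-level comparisons in the third. Table 2.6.1 shows that ASRM is also collected weekly.

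The only other statement on imputation is in Section 3.3: "Analyses will use observed data only (i.e. without imputation").

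**The concern.** Filling a gap from the average of the answered items is defensible when few items are blank, and becomes less so as more are blank. Four rows follow that logic by setting a ceiling on missing items. The ASRM and GAD7 rows set a floor instead. Taken literally, they accept questionnaires that are mostly empty and leave nearly complete ones without a total.

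Section 5.2 judges reliable change participant by participant, against 1.96 times the standard error of the difference. A total built from one or two answers can therefore create or hide a deterioration in the primary safety outcome. Whoever programs the table must either apply a rule that makes no sense or depart from the SAP and choose a cut-off, possibly after seeing the data.

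**Working it through.** The plan gives no figure to reproduce here. The check concerns the direction of an inequality.

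**Inputs.** The thresholds come from Section 5.1.1. The item counts for the GAD-7 (7) and PHQ-9 (9) are read from the instrument names. The ASRM item count is not in the SAP; 5 is assumed, with 4 and 10 as a range. Item scores of 0–3 (GAD-7) and 0–4 (ASRM) are also assumed.

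**Step 1: which questionnaires are imputed.** For a scale of k items with m blank (1 ≤ m ≤ k − 1), the stated rule imputes when m > 2. The PHQ9 direction imputes when m ≤ 2.

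| Scale | Imputed if m > 2 (as written) | Imputed if m ≤ 2 (PHQ9 direction) |
|---|---|---|
| GAD-7 | 3–6 of 7 blank (43–86%) | 1–2 of 7 (14–29%) |
| ASRM, k = 5 | 3–4 of 5 (60–80%) | 1–2 of 5 (20–40%) |
| ASRM, k = 4 | 3 of 4 (75%) | 1–2 of 4 (25–50%) |
| ASRM, k = 10 | 3–9 of 10 (30–90%) | 1–2 of 10 (10–20%) |

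The inversion does not depend on the ASRM item count. By comparison, the PHQ9 row never imputes with more than 2 of 9 blank (22%).

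**Step 2: the extreme case.** The imputed total is k × (sum of answered items) / (k − m). For a GAD-7 with m = 6 and a single answer x, this is 7x. With x = 0, 1, 2 or 3, the total can only be 0, 7, 14 or 21.

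**Step 3: how noisy the imputed totals are (illustration).** In a simulation of 200,000 respondents per scale, with one-factor items and loading 0.7, the root mean squared error of the imputed total against the true total was:

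| Items blank | 1 | 2 | 3 | 4 | 5 | 6 |
|---|---|---|---|---|---|---|
| ASRM (5 items; total SD about 4) | 0.95 | 1.55 | 2.33 | 3.79 | – | – |
| GAD-7 (total SD about 5) | 0.82 | 1.27 | 1.74 | 2.32 | 3.17 | 4.93 |

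The rule as written imputes only from the third column onward. At the far end the error is about as large as the scale's own SD. A repeat under three assumed item distributions per scale gave similar results. For ASRM the error was 0.8–1.0 with 1 blank and 3.2–4.0 with 4 blank, against an SD of 3.2–4.4. For GAD-7 it was 0.8 with 1 blank and 4.9–5.1 with 6 blank.

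**Step 4: effect on a rate with N = 12.** One participant wrongly classified moves the rate by 1/12 = 8.3 points. A lost participant also shrinks the denominator. With d deteriorators among 12:

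- Losing a non-deteriorator shifts the rate by d/11 − d/12 = d/132, which is 0, 0.8 or 1.5 points for d = 0, 1 or 2.
- Losing a deteriorator shifts it by d/12 − (d − 1)/11 = (12 − d)/132, which is 8.3 points for d = 1 and 7.6 for d = 2.

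So 8.3 points is the size for a false case and the upper bound for a lost one.

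**The case against.** The best reply is that this is an obvious slip which a careful analyst would query. Section 5.2 contains a similar one, where reliable-change scores above 1.96 are called significant at p greater than .05. The study is small and mainly descriptive (Section 3.1). The primary benefit outcome uses PHQ and ALS, which are unaffected, and safety also rests on adverse events and four other scales. The secondary ASRM outcome compares period means, so one bad weekly score is diluted.

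Much of this is fair, but it bears on how likely harm is, not on whether the rule is wrong. The dilution does not extend to the ASRM and GAD deterioration rates or to the secondary GAD outcome, which compare single time points.

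Three limits stand:

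- The simulation rests on assumed item counts, score ranges and one loading. It says nothing about how often items will be blank in this trial, and it is not translated into a misclassification rate.
- That a score with 1 or 2 blanks is lost follows from the absence of any rule for it, not from an explicit statement.
- The SAP does not show which cut-off was intended.

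Section 3.3 does not rescue the rule. It sits under study populations and leaves the two rows uncorrected. If it overrode item-level imputation, all six rules in the table would be void.

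A fault in reading the PDF is unlikely, because the other inequality signs in the same column came through correctly. The source PDF was not available to confirm this.

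**Conclusion.** The concern holds. The ASRM and GAD7 rows state a rule that yields wrong scores if followed, runs against the other four rows, and is not corrected elsewhere in the SAP. The direction error needs no outside assumption for GAD-7 and holds for ASRM at every length tried. The numerical consequence is bounded, not estimated: up to 8.3 percentage points per affected participant if all 12 contribute, at an unknown frequency of blank items. Because both scales feed a primary safety outcome, it must be corrected before analysis.

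**What to change.** Reverse the inequality in the two cells of the Section 5.1.1 table and state that the total is set to missing when more items are absent. Two cut-offs are workable:

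- **At most 1 missing item** is the plain reversal of the sign. It allows 1/7 = 14% on the GAD-7 and 1/5 = 20% on a 5-item ASRM, both inside the 25% limit set for the ALS.
- **At most 2 missing items** matches the PHQ9 row. It allows 29% on the GAD-7 and 40% on a 5-item ASRM, both above that limit.

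The first is the safer choice for ASRM; either would serve for GAD-7. The authors should confirm the cut-off they intended before analysis. The cost is an edit to two cells, and a few questionnaires with many blanks will have no total.

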5.2. Analysis methods

In relation to aim (i) which concerns safety, feasibility and acceptability, we will report descriptively the number of adverse events, serious adverse events and the number of each judged to be related to the therapy, and rates of reliable deterioration. We will also report the number of participants experiencing at least one adverse event. We will report the number of participants expressing an interest in the study, giving consent, found to be eligible, commencing treatment and completing treatment, as well as the median, mode and range of sessions attended during treatment. We will report descriptively the average and distribution of scores on the therapy feedback items.

Aim (ii) investigates the potential for clinical efficacy. Analytical approaches to examining clinical outcome data in a case series can include visual and statistical methods, and focus on change at the

level of the individual participants, or aggregated across the sample. In this population the extent to which a stable baseline can be expected is not clear, therefore we will use visual methods combined with descriptive statistics (Lane & Gast, 2013) to allow examination of overall patterns of change. Assessment of symptom scores over time for each participant will be made by two independent raters who will then reach consensus on each pattern (improvement, deterioration, no change) and will include calculation of overlap between weekly scores in the baseline, therapy and post-therapy periods through calculation of baseline-corrected Tau following the steps described by Tarlow, (2017) whereby the baseline trend is removed before performing Tau analysis if it is statistically significant. In terms of statistical analyses, reliable change index scores (RC) will be calculated to assess for the statistical reliability of the changes on the clinical outcome variables between each phase of the case-series for each participant. A participant is said to show reliable change when their change score from pre to post therapy is more than 1.96x the standard error of the difference (Ferguson, Robinson, & Splaine, 2002), the latter being calculated using values from the literature in most comparable samples. RC scores greater than the z-score level of 1.96 are statistically significant at $p > .05$. We will report the proportion of participants showing: i) reliable improvement /no change / reliable deterioration in the clinical outcome measures; ii) improvement that is both reliable and clinically significant, where clinically significant change is defined as the scoring falling below / above the established threshold for clinical significance (dependent upon whether decrease / increase in score is considered to represent clinical improvement). Where established thresholds are not available we will use Jacobson and colleagues (1984) criteria a, b or c to define clinically significant change depending upon the information available in the literature for each measure. Criterion a requires the participant's score to have moved more than 2 SDs from the mean of the patient group, criterion b requires the participant's score to have moved to within 2 SDs of the unaffected reference group, and criterion c requires the score to have moved closer to the mean of the unaffected group than to the mean of the clinical group.

Using continuous scores on the outcome measures, effect sizes and 95% confidence intervals will be computed to obtain a preliminary estimate of the potential magnitude of change on each measure from baseline to post therapy and pre to post therapy: these statistics can be used by other researchers in future meta-analyses seeking to synthesise the outcomes of a number of studies (Manolov et al., 2022).

Relevant to aim (iv) which is to develop an initial therapy competence and adherence measure, using the version of the measure developed during the case series two therapists will independently assess the same 12 recordings of therapy sessions to estimate inter-rater agreement on the measure by calculating the intraclass correlation coefficient using a two-way random effects model, for both consistency and absolute agreement.

Planned secondary analyses

Relevant to aim (i), qualitative interviews will be audio-recorded and then transcribed. Participants' responses will be read closely and coded using a framework approach. Data relevant to each category will be compared and summarised and non-conforming cases examined closely in order to

understand similarities and differences in perspective. Interview recordings will be transcribed by a member of the study team, or a suitable individual working with the team who has signed a confidentiality agreement.

Relevant to aim (ii), data from the momentary assessment blocks will be used to examine change in mood variability from the baseline to post therapy phases, by calculating mean variability (SD) across each of the two blocks.

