2.1. Design

Two cohort randomised multiple baseline ABA case-series design. Randomisation is to a wait period of 3,4 or 5 weeks before starting therapy. The intervention is an adapted form of behavioural therapy delivered on a one-to-one basis over up to 22 sessions, over up to 7 months.

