2.2. Randomisation

Participants will be randomised to different baseline assessment lengths (between 3 and 5 weeks). The randomisation sequence will be generated and administered by an individual independent of the study on a 1:1:1 allocation sequence (block randomisation) with one block per cohort of 6. The randomisation sequence will be generated by [name] (Exeter CTU statistician) and then passed to a researcher independent of the project and research team. The research team will contact this person after eligibility is confirmed for each participant to obtain the allocation next in the sequence.

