2.3. Sample Size

It is good practice to have at least 3 replications of the pattern of change across different cases (inter-case replication) as well as more than one therapist treating patients. Patients are treated in two cohorts within the current study: a total of 12 participants, 6 in each cohort, would allow these criteria to be met within each cohort (with at least two therapists seeing patients in each cohort).

Participants who exit the study after randomisation, but before completing the pre-therapy measures will be replaced (with new random allocation) to give N=12 commencing the therapy period.

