2.6. Timing of outcome assessments

Table 2.6.1: Timings of outcome assessments

Measure	Intake	Pre-treatment	Weekly*	Immediately post-treatment	7 months (30 weeks) post treatment onset	6 months (26 weeks) post end of treatment
PHQ-9	X	X	X		X	
ASRM	X	X	X		X	
Depression-elation subscale of ALS short form			X			
ALS short form	X	X			X	
Brief QoL.BD	X	X			X	
BRQ	X	X			X	
GAD-7	X	X			X	
Momentary assessment block	X			X		
Post therapy feedback questionnaire				X		

Post therapy interview				X		
Booster sessions feedback questionnaire						X

Data that are collected outside of the time-windows shown in Table 2.6.2 will be excluded from the primary analysis but included in a secondary sensitivity analysis (quantitative measures) or will be included but with discrepancy in collection time noted (qualitative).

Table 2.6.2: Time windows for data collection per assessment point

Timepoint	Data collection window	Notes
Intake (prior to randomisation)	Not applicable	Required for eligibility
Weekly from intake to 3 weeks post end of therapy (randomisation occurs between weeks 0 and 1)	+7 days	late returns within 5 days will be accepted and subsequent time point will continue as planned
5x per day for 14 days starting day after eligibility confirmed; second 14 day block starting day after end of treatment confirmed (randomisation occurs during first week of block 1)	+3 hours	late returns within this window will be accepted and subsequent timepoint will continue as planned
Pre-treatment (post randomisation)	+28 days	
7 months post pre-treatment	+28 days	
Post end of treatment	+28 days	
6 months post end of treatment	+28 days	

3. Statistical principles

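### Baseline trend is removed before Tau only if significant, but with 3 to 6 baseline scores that test can rarely or never reach significance, and whether it can depends on the randomised wait

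*SAP*

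**What the plan says.** Section 5.2 of the SAP has two independent raters classify each participant's course as improved, deteriorated or unchanged. Their assessment includes "calculation of overlap between weekly scores in the baseline, therapy and post-therapy periods", measured by baseline-corrected Tau, "whereby the baseline trend is removed before performing Tau analysis if it is statistically significant". The procedure is taken from a cited 2017 paper. The SAP gives no significance level, sidedness, test version, minimum number of points or fallback for the trend test.

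The baseline length is set by section 2.1: "Randomisation is to a wait period of 3,4 or 5 weeks before starting therapy". Table 2.6.2 sets the frequency: "Weekly from intake to 3 weeks post end of therapy (randomisation occurs between weeks 0 and 1". The SAP does not say whether the intake score counts as a baseline point.

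Section 5.2 also gives the reason that trend matters here: "In this population the extent to which a stable baseline can be expected is not clear".

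**The concern.** Someone already improving before therapy starts will show little overlap between baseline and later scores even if therapy does nothing. Trend correction is meant to guard against this. Making it conditional on significance works only if the test can detect a trend, and a rank test on 3 to 6 points has almost no room to do so.

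Two things are at stake. Pre-therapy drift would stay in Tau for nearly everyone, in a population whose baseline stability the SAP itself doubts. And the same drift could be removed for a participant randomised to a long wait but not for one randomised to a short wait, for a reason unrelated to the drift.

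**Working it through.** The SAP states no figure for this test, so there is nothing to reproduce.

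**Inputs from the SAP**
- Wait of 3, 4 or 5 weeks (section 2.1), scored weekly from intake (Table 2.6.2). Baseline points: 3/4/5, or 4/5/6 with intake.
- Allocation "on a 1:1:1 allocation sequence (block randomisation) with one block per cohort of 6" (section 2.2) and "a total of 12 participants, 6 in each cohort" (section 2.3). Per wait length: 6 ÷ 3 = 2 per cohort, 2 × 2 = 4 of 12 overall, before any replacements.

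**Assumption.** A two-sided 5% test, in line with the 1.96 criterion that section 5.2 uses for reliable change ("RC scores greater than the z-score level of 1.96 are statistically significant at" the conventional level).

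**Step 1: smallest attainable p.** With n untied scores there are n! equally likely orderings under no trend, and two of them are perfectly monotone. The smallest exact two-sided p for Kendall's tau is therefore 2/n!. The next column comes from enumerating all orderings.

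| n | 2/n! | p with one discordant pair | Significant at two-sided 5%? |
|---|---|---|---|
| 3 | 2/6 = 0.333 | 1.000 | never |
| 4 | 2/24 = 0.083 | 0.333 | never |
| 5 | 2/120 = 0.0167 | 0.083 | only if perfectly monotone |
| 6 | 2/720 = 0.0028 | 0.0167 | with at most one discordant pair |

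At n = 6, two discordant pairs give 0.056. An otherwise monotone 5-point series with one tied pair gives 0.033.

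**Step 2: who could never be corrected.**
- 3/4/5 points: the 3- and 4-week groups, 4 + 4 = 8 of 12.
- 4/5/6 points: the 3-week group, 4 of 12.

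**Step 3: sensitivity to the unstated test version (perfectly monotone series).**

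| Version | n = 3 | n = 4 |
|---|---|---|
| Exact, two-sided | 0.333 | 0.083 |
| Exact, one-sided | 0.167 | 0.042 |
| Normal approximation, continuity-corrected, two-sided | 0.296 | 0.089 |
| Normal approximation, uncorrected, two-sided | 0.117 | 0.0415 |

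Three points fail at 5% in every version. A perfect 4-point trend passes only one-sided, by the uncorrected approximation, or with the level raised to 10%.

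**Step 4: how often correction is triggered when the trend is real.** Simulation of a linear fall of 1 PHQ-9 point per week plus independent normal error, exact two-sided 5% rule. The slope and SDs are assumptions.

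| Weekly noise SD | n = 3 | n = 4 | n = 5 | n = 6 |
|---|---|---|---|---|
| 2.5 (slope 1/2.5 = 0.40 SD per week) | 0% | 0% | 5% | 10% |
| 1.5 (slope 1/1.5 = 0.67 SD per week) | 0% | 0% | 12% | 26% |

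A steeper trend helps only the longer baselines: at 1 SD per week the rates are 0%, 0%, 25% and 52%; at 2 SD per week, 0%, 0%, 71% and 96%.

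**The case against.** **The test version is unknown.** The SAP defers to a published procedure and fixes neither level nor sidedness. With an uncorrected normal approximation and intake counted, every wait group could in principle be corrected. For the Step 4 trend, correction would then be triggered in about 14% (SD 2.5) to 23% (SD 1.5) of 4-point baselines and 25% to 52% of 6-point baselines. This stands. The counts of 4 and 8 of 12 depend on the assumed test, and a flat statement that the 3-week group can never be corrected goes further than the document allows. Even so, a true trend would be missed in most 4-point baselines, and an outcome that turns on unstated choices is a reason to settle the text.

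**The number of points is unsettled.** Table 2.6.1 also lists PHQ-9 at pre-treatment. If that score is separate from the weekly series and counts, each baseline gains a point. Section 5.2 speaks of weekly scores, which argues against this but does not exclude it. Missed weekly returns would reduce the counts.

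**Little rests on Tau.** A reader might infer that the trial's benefit result is compromised. The SAP does not support that. Section 5.1 defines potential benefit by rates of reliable, and reliable and clinically significant, change between baseline-period and post-therapy means. Tau is one input to a per-participant visual judgement in which the raters can see the plotted baseline, and no pooling of Tau or comparison by wait length is planned. This stands and limits the severity.

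**Wait length does not decide who is corrected.** A reader might also infer that it does. It limits who can be corrected; within a group that can be, the data decide.

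**Correcting everyone has its own weakness.** A slope from 3 to 6 points carried across roughly 30 weeks is fragile and may leave the scale. That is a fair reason not to make corrected Tau the sole measure, and it does not rescue the significance condition.

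**Conclusion.** The point holds with limits. As written, the rule makes trend removal depend on a test that, at these baseline lengths, is either unable to reach significance or seldom does, and whether it is able depends on the randomised wait.

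The firm part is that 3 points fail at 5% under every version checked. The conditional part is that 4 points also fail under an exact two-sided 5% test, so that 4 of 12 participants (8 of 12 if intake is not counted) are beyond correction. The trigger rates of 5–12% at 5 points and 10–26% at 6 rest on the assumed slope, SDs and exact test.

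The consequence is confined to the Tau input to the raters' assessment under aim (ii). It should be fixed before analysis, but it does not threaten the reliable-change outcome.

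**What to change.** In section 5.2, delete the condition that the trend be significant. For every participant, report uncorrected Tau and baseline-corrected Tau side by side, with the baseline tau and baseline slope, and give both to the two raters. State which scores make up the baseline, in particular whether intake and pre-treatment scores count. Add a sentence that corrected values carry a slope from 3 to 6 points over about 30 weeks and are to be read with caution.

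The cost is a few sentences of SAP text and extra columns in a 12-row table; no new data are needed. The downside is that raters and readers have two Tau values per participant, which may disagree. Settling this before the scores are analysed keeps the choice from being made with results in view.

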1.1. Background and rationale

Bipolar Spectrum Disorders typically involve periods of depression, and periods of very high energy and mood (hypomania or mania). Bipolar Disorders (BDs) are common, affecting around 1 in 20 people at some point in their lifetime. They can be very distressing and disruptive to the people who experience them, and for friends and relatives. Many people with these conditions have mood issues outside depressive or manic episodes. Often these issues include ongoing low mood, and/or frequent swings in mood or emotions. These are sometimes called “inter-episode bipolar symptoms” (IEBS).

There are psychological (talking) therapies designed to help people with Bipolar Disorders, but these tend to be aimed at preventing a relapse of depression or mania, or they are aimed at helping people recover from a period of depression. There is no universally accepted talking therapy for helping people who have ongoing low mood or mood swings in between full episodes.

The aim of this study is to provide an initial evaluation of a psychological therapy designed to address these ongoing symptoms. A total of 12 people, in two consecutive cohorts of six to allow refinement of the therapy in between, will be offered the therapy and will be randomly allocated to a waiting period of 3-5 weeks after their baseline assessment. They will then repeat some of the assessment measures and commence the therapy which will be delivered over a period of approximately seven months. At the end of therapy, they will complete the set of assessment measures again and complete a three week post therapy monitoring period. Throughout the baseline, therapy and post-therapy periods they will be invited to complete some brief measures of symptoms on a weekly basis. At two points (during the first two weeks of the baseline period and of the post therapy period) they will be invited to complete a block of mood and activity monitoring when they will be asked briefly about mood and key activities five times per day for 14 days. Views on the acceptability of the therapy will be collected from participants in terms of numerical ratings of acceptability, written feedback and through interviews.

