3.1. Confidence intervals and p-values

In accordance with the feasibility aims of the study, all outcomes will be reported descriptively. All quantitative outcomes are continuous measures and will be reported at each timepoint measured using the mean and standard deviation. Descriptive analyses will include all reported data collected within the time window specified (Section 2.6). In addition, as a sensitivity analysis, we will also report descriptive analyses including all reported data (irrespective of whether within the time window).

In accordance with the aims of the study, which primarily concern feasibility, inferential statistical tests will be limited. Where these are carried out (calculation of pre-post change in terms of reliable and reliable and clinically significant change, and group-level, pre-post effect size), effect sizes and two-sided 95% and 90% confidence intervals will be reported.

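### The momentary mood ratings are summarised only by an SD, which captures the size of mood variation but not its course from rating to rating; a successive-difference index should be reported beside it

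*SAP*

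**What the plan says.** SAP section 5.1 defines the fourth secondary outcome as follows: "Mood instability will be measured (in addition to the ALS) by a visual analogue scale of mood at five timepoints per day for 14 days". One such block is run before therapy and one after it. The SAP adds: "This allows for the calculation of mood instability before and after therapy".

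SAP section 2.6, Table 2.6.2, fixes the schedule of the first block, "5x per day for 14 days starting day after eligibility confirmed", with a second 14-day block after treatment ends. Returns up to 3 hours late are accepted.

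SAP section 5.2, under planned secondary analyses, gives the only analysis of these ratings: "data from the momentary assessment blocks will be used to examine change in mood variability from the baseline to post therapy phases", and this is done "by calculating mean variability (SD) across each of the two blocks".

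The background in section 1.1 describes the target symptoms: "Often these issues include ongoing low mood, and/or frequent swings in mood or emotions". Section 3.1 sets the status of the results: "In accordance with the feasibility aims of the study, all outcomes will be reported descriptively".

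**The concern.** The outcome is called instability where it is defined and variability where it is analysed, and the statistic chosen belongs to the second term. An SD does not change when the ratings are put in a different order. How often mood swings is a property of that order, and frequent swings are one of the two problems that the SAP says people with these conditions have between episodes. No statistic in the SAP uses the order of the momentary ratings, although these are the only within-day data in the study.

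A whole-block SD also grows with any gradual shift in mood over the fortnight. The SAP allows for this elsewhere: section 5.2 doubts that a stable baseline can be expected, and removes a significant baseline trend from the weekly scores before the Tau analysis. The momentary ratings have no such protection.

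At stake is how the before-after contrast is read. Swings could become slower or faster with no change in SD, and a steady recovery within one block could look like greater instability.

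**Working it through.** **Inputs.** From the SAP: 5 ratings a day × 14 days = 70 scheduled ratings per block (section 2.6), summarised by an SD (section 5.2). The SAP reports no figure for this outcome, so there is none to reproduce. It also gives no scale range, autocorrelation or expected drift, so all values below are illustrative assumptions.

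**Formulas.** RMSSD = square root of the mean squared difference between successive ratings. For a stationary series with lag-1 correlation r, RMSSD = SD × √(2(1 − r)).

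**1. Same values, different order.** Take 70 equally spaced values from 20 to 80, with step 60/69 = 0.87.
- Steady rise: SD 17.70, RMSSD 0.87.
- Alternating low and high: SD 17.70, RMSSD 30.01.

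The RMSSD differs about 35-fold (30.01/0.87) and the SD not at all. These RMSSDs use all 69 successive differences. Dropping the overnight gaps leaves 4 × 14 = 56 differences and hardly changes them: every step of the rise is still 0.87, and every alternating step is about 30.

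**2. Equal SD, different persistence.** √(2(1 − r)) is 1.41 at r = 0, 1.00 at r = 0.5, 0.63 at r = 0.8 and 0.45 at r = 0.9. From r = 0 to r = 0.9 the RMSSD changes about threefold (1.41/0.45) at the same SD.

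**3. The two indices can disagree in direction.** Let the SD fall from 15 to 12 while r moves from 0.8 to 0.3.
- Before: 15 × √0.4 = 9.5.
- After: 12 × √1.4 = 14.2.

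The SD reads as improvement, the RMSSD as worsening.

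**4. Drift.** A smooth rise from 0 to 30 over 70 ratings gives SD 8.85 and RMSSD 30/69 = 0.43. With independent fluctuation of SD 15 added, the SD becomes √(15² + 8.85²) = 17.4, which is 16% above 15. This is the more realistic size of the drift effect.

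**5. If the SD is a mean of daily SDs.** In the series of step 1, the mean daily SD is 1.37 for the rise and 16.45 for the alternation, so slow drift and rapid swings are separated. Order within the day is still lost. The ratings 20, 35, 50, 65, 80 and the ratings 50, 20, 80, 35, 65 both have SD √(2250/4) = 23.7. Their RMSSDs are 15 and √(7425/4) = 43.1.

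**6. Limit of the within-day RMSSD.** Let mood be flat within each day and alternate between 20 and 80 on successive days. The within-day RMSSD is 0, and the block SD is √(70 × 900/69), about 30. Neither index is sufficient alone.

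**The case against.** A reader might infer that the planned outcome does not measure instability at all. The documents do not support that. By the identity above, RMSSD is proportional to SD when r is fixed, so the SD carries the amplitude part of instability. The SAP sets no time scale for the swings it describes, and section 5.2 calls its quantity variability and computes a measure of variability.

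Nor does the text fix the whole-block reading. It is the natural one, but the wording could also mean an average of daily SDs, and step 5 shows that this would largely deal with drift across days. It would not restore order within the day, and the ambiguity itself needs settling.

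A reader might also infer that RMSSD should replace the SD. Step 6 shows why it should not.

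The consequences are limited. The analysis is a planned secondary one in 12 participants, reported descriptively. The Affective Lability Scale (ALS) also covers mood instability: its depression-elation subscale is collected weekly, and an ALS mood scale is part of primary outcome 3. The progression thresholds are assessed once participants have attended at least eight of up to 22 sessions or have discontinued. For those still in therapy, that is before the post-therapy block. The drift and persistence examples are extremes, and drift distorts the contrast only if it differs between the two blocks.

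All of this stands and limits the weight of the point. It does not remove it. Section 5.1 adds the momentary measure to the ALS, which is given at most weekly and cannot show change between ratings within a day.

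**Conclusion.** The point holds as a modest, inexpensive improvement. The SAP names mood instability as an outcome, but specifies for the momentary ratings only a measure of dispersion. On the whole-block reading, that measure cannot tell rapid swings from slow drift. On the daily reading, it still ignores order within the day. How far this would alter the trial's results cannot be derived from the SAP. The 35-fold and threefold contrasts show what an SD cannot see and are not forecasts. The order-invariance of the SD rests on no assumption; the sizes rest on the assumed values, correlations and drift.

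**What to change.** In SAP section 5.2, planned secondary analyses:
- Add, for each participant and block, the RMSSD between successive ratings within the same day, reported beside the SD as an index of instability. Use only pairs of consecutive prompts that were both answered, and exclude overnight gaps.
- State the rule for missed prompts and for prompts answered late within the 3-hour window, since late answers make the intervals unequal.
- Keep the SD and the block mean, so that amplitude, level and day-to-day swings remain visible.
- State whether the SD is taken over the whole block or is the mean of daily SDs, and use the terms instability and variability consistently in sections 5.1 and 5.2.

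The cost is a few sentences and a few lines of code on ratings already planned. A missed prompt loses up to two of the 56 possible within-day differences in a block, and there is one more descriptive index to report.
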